5.4.3 Adherence

Adherence will be recorded by the patients' diary.

5.4.4 Prior and Concomitant Diseases

Relevant additional diseases present at the time of informed consent are regarded as concomitant diseases and will be documented on the appropriate pages of the case report form (CRF).

Abnormalities which appear for the first time or worsen (intensity, frequency) during the study are adverse events (AEs) and must be documented on the appropriate pages of the CRF.

5.4.5 Prior and Concomitant Medication

The treatment of accompanying illnesses not subject to the exclusion criteria is permissible if this is not expected to have any effect on the outcome measures used in this study and to interfere with the study medication.

In particular, the following drug groups are **not permitted** as concomitant medication:

Systematically administered glucocorticoids or other immunosuppressive drugs

If concomitant drugs are administered, these must be recorded in the patient file and in the CRF.

5.4.6 Adjustments to dosage of the IMP in the individual study subject Dosage is adjusted according to individual body surface area.

5.4.7 Dose modification

Dosage modifications, if treatment related toxicities occur during the study.

a. Mycophenolate mofetil

Adverse events concerning gastrointestinal tract

- vomiting (defined as a frequency of more than 2 times per day, lasting for ≥48 hours)
 - Split daily mycophenolate mofetil dose into up to 4 doses
 - If there is no improvement within 48 hours reduce mycophenolate mofetil dose by 50% in addition
 - o In case of repeated episodes (≥3) or prolonged vomiting (>6 days) discontinuation of mycophenolate mofetil by investigator
- diarrhea (defined as a frequency of more than 3 watery stools per day, lasting for ≥48 hours)
 - Split daily mycophenolate mofetil dose into up to 4 doses
 - If there is no improvement within 48 hours reduce mycophenolate mofetil dose by 50% in addition
 - o In case of repeated episodes (≥3) or prolonged diarrhea (>6 days) discontinuation of mycophenolate mofetil by investigator
- nausea (defined by duration >5 days and medical declaration of association to mycophenolate mofetil)
 - Split daily mycophenolate mofetil dose into up to 4 doses
 - If there is no improvement within 72 hours reduce mycophenolate mofetil dose by 50% in addition

Adverse events concerning blood count

- hemoglobin concentration of ≤10 g/dL at visit 2 or visit 3
 - Reduction of daily dose of mycophenolate mofetil by 50%, control of hemoglobin concentration after 7-10 days
 - Upon resolution (hemoglobin concentration ≥10g/dL), resumption of maintenance study drug dosing should be attempted
 - In case of hemoglobin concentration ≤8 g/L discontinuation of mycophenolate mofetil by investigator
- leucocyte count of ≤4.000/µl at visit 2 or visit 3
 - Reduction of daily dose of mycophenolate mofetil by 50%, control of leucocyte count after 7-10 days
 - Upon resolution (leucocyte count ≥4.000/μL), resumption of maintenance study drug should be attempted
 - In case of leucocyte count ≤2.500/μL discontinuation of mycophenolate mofetil by investigator
- thrombocyte count of ≤100.000/µL at visit 2 or visit 3
 - Reduction of daily dose of mycophenolate mofetil by 50%, control of thrombocyte count after 7-10 days
 - Upon resolution (thrombocyte count ≥100.000/μL), resumption of maintenance study drug should be attempted
 - o In case of leucocyte count ≤50.000/μL discontinuation of mycophenolate mofetil by investigator

Adverse events concerning infections

- Severe bacterial infection or severe verified viral infection (e.g. Herpes zoster, Varicella, EBV, CMV,...)
 - Stop of mycophenolate mofetil medication until clinical resolution. Then restart mycophenolate mofetil with 50% of the last maintenance dose

Other adverse events

- recurrent infections/ suspected hypogammaglobulinemia at visit 2 or visit 3
 - Determine serum immunoglobulins. If newly diagnosed hypogammaglobulinemia is confirmed: discontinuation of mycophenolate mofetil by investigator
- Pulmoniary symptoms, e.g. cough or dyspnoe at visit 2 or visit 3
 - Physical examination, if bronchiectasia is suspected, performance of chest X-ray.
 If bronchiectasia confirmed: discontinuation of mycophenolate mofetil by investigator

In any adverse event due to mycophenlate mofetil and in individual situations which are not defined clearly in the study protocol (5.4.7.) the investigator may decide, if discontinuation of mycophenolate mofetil should be temporary or permanent. The Clinical Project Management supports the investigator in decision-making.

b. Glucocorticoids

Glucocorticoids are given according to center practice, since this is the control intervention

 In case of diabetes mellitus (glucocorticoid-induced, primary manifestation or preexisting) prednisone is allowed to be given daily instead of alternate-day (with the same cumulative dose, e.g. 10 mg per day instead of 20 mg alternate-day) in order to falicitate management of the diabetes.

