2.2 Secondary Objectives and Secondary Endpoints

Secondary endpoints are divided into five items:

- 1. Course of the disease as described by the following criteria
 - a. Time from remission to first relapse
 - b. Number of relapses during follow-up
 - c. Mean relapse rate per patient and year
 - d. Number of frequent relapsers
 - e. Time from remission to intensification of immunosuppressive treatment with other drugs due to glucocorticoid-induced toxicity
 - f. Rate of patients who require more intense immunosuppressive treatment
- 2. Glucocorticoid-associated toxicity:
 - a. Cumulative prednisone dose as mg/m²
 - b. As there is no validated score for glucocorticoid-induced toxicity, each item is registered separately. At visits 1-8, body mass index, arterial hypertension, and growth failure will be checked for quantitative influence, striae, hypertrichosis, acne, and psychological disturbances by yes or no for qualitative influence. Additionally, at visits 1, 5, and 8, patients will be checked for cataract and glaucoma (by yes or no).

.....

- 3. Mycophenolate mofetil-associated toxicity: At all visits, patients will be checked for known side effects of MMF, especially diarrhea, blood cell count disturbance, and infections.
- 4. Health-related quality of life, which is impaired in children with nephrotic syndrome [21], will be measured with a validated questionnaire (DISABKIDS) at visits 1/5/8.
- 5. Days missing school attendance and days of hospitalization will be documented as a measure for the impact of the disease on everyday life.

It is expected that MMF-based regimen will avoid acute and long-term glucocorticoid-associated toxicity and is therefore superior regarding the benefit/risk ratio. However, this will not be tested confirmatorily since there exists no endpoint/score summarizing the different aspects of side effects.

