The persons having care and custody of the child are instructed to interpret the results of the Albustix[®] and are instructed to react as described. In doubt the persons having care and custody of the child are encouraged to contact the study center early.

Albustix™	Interpretation	Consequence
Negative	No relapse	Nothing to do
Trace		
30 mg/dL = +	doubtful value	 Daily weight investigation for edema (yes/no) The urine protein/creatinine ratio (Up/c) or a specimen of a urine collection has to be analyzed, if 1+ appears for 3 days or 1+ is combined with ≥2+ within 3 days.
100 mg/dL = ++		
300 mg/dL = +++	Relapse, if detected on 3 consecutive days	Contact study center
≥2000 mg/dL		
= ++++		

Visit 2

Visit 2 is scheduled at 4 weeks after visit 1 (± 5 days).

At visit 2, the history since visit 1 is documented, especially if one or more relapses occurred since visit 1.. In case of a relapse, date of first day of relapse (definition fulfilled) is documented. For each relapse, it is documented, according to which criteria the relapse was diagnosed: Albustix $\geq 2+$ (>30mg/dL) for 3 consecutive days, Spot urine: Up/c ratio ≥ 2 g/g, or collecting urine: Up excretion of ≥ 40 mg/m² BSA/h. If the relapse was treated, the medication is recorded. Further, date of remission is documented (see definitions). In order to document possible trigger factor infections during relapse (e.g. respiratory tract infection, gastroenteritis) and vaccinations within two weeks prior to the relapse are recorded, too. All information from the diary (days missing school attendance, days of hospitalization since last visit are recorded. According to diary and patients inquiry adherence to study medication is assessed (Reduction of study medication > 50%?, Pause of study medication > 3 days?).

Side effects of the treatment are retrieved in yes/no manner (Behavioral disturbances since visit 1: child feels sad, anxious, irritable, as well as euphoric state, aggressive state, nausea, vomiting (defined as a frequency of more than 1 times per day), diarrhea (defined as a frequency of more than 4 loose stools daily), headache, muscle weakness, any new infection).

Application of any current medication (other than immunosuppressive agents) is documented.

The event of renal biopsy since last visit is recorded with histology.

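### The visit-form definition of diarrhea is narrower in stool count than the MMF dose-modification definition, so a child whose MMF is modified for diarrhea can be recorded as having none

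*Protocol*

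**What the plan says.** Section 5.4.7 gives the definition on which the site acts: "diarrhea (defined as a frequency of more than 3 watery stools per day, lasting for ≥48 hours". Three steps follow. The first is "Split daily mycophenolate mofetil dose into up to 4 doses". The second is "If there is no improvement within 48 hours reduce mycophenolate mofetil dose by 50% in addition". The third is "In case of repeated episodes (≥3) or prolonged diarrhea (>6 days) discontinuation of mycophenolate mofetil by investigator".

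The visit descriptions in Section 6.1 contain a yes/no list of side effects, repeated at all eight visits. Its diarrhea entry reads "diarrhea (defined as a frequency of more than 4 loose stools daily". It has no minimum duration and records no stool count.

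Section 2.2, item 3 sets the MMF-toxicity endpoint: at every visit, "patients will be checked for known side effects of MMF, especially diarrhea, blood cell count disturbance, and infections". It gives no stool count of its own. The synopsis also names diarrhea first under MMF-associated toxicity.

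**The concern.** The threshold for changing treatment is lower, in stools per day, than the threshold for recording that the symptom occurred. Some diarrhea serious enough for the protocol to require a change in MMF therefore does not qualify as diarrhea on the visit form. Section 2.2 defines nothing else, and the side-effect item is the only diarrhea check described at every visit, so the natural reading is that the endpoint rests on that item.

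Two things are at stake. First, the visit-based diarrhea result would not reconcile with the reported MMF reductions and discontinuations for diarrhea. Secondly, the loss is permanent. A yes/no answer cannot be reclassified later, and the diary content listed under visit 1 does not include stool counts. Section 2.2 expects MMF to come out ahead on benefit and risk, so a leading MMF toxicity should be recorded in a way that agrees with the protocol's own rule for acting on it.

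**Working it through.** No figure stated in the protocol bears on this point, so there is none to reproduce. The check compares two thresholds.

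**Inputs**
- Dose rule (Section 5.4.7): more than 3 watery stools a day, so 4 or more, for at least 48 hours.
- Visit item (Section 6.1, visits 1 to 8): more than 4 loose stools a day, so 5 or more, with no duration.
- Assumption: a watery stool counts as a loose stool on the form.

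**Comparison by stools per day** (duration criterion taken as met)

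| Stools per day | Dose rule met | Visit item |
|---|---|---|
| 3 or fewer | no | no |
| 4 | yes | no |
| 5 or more | yes | yes |

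The two disagree at exactly one value, 4 a day.

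**Can a child at 4 a day reach each dose step?** Suppose 4 watery stools daily without improvement, and suppose the 48-hour wait starts when the dose is split.
- After 48 hours the definition is met and the dose is split.
- After 48 + 48 = 96 hours, day 4, the 50% reduction applies.
- Beyond 6 days, discontinuation applies.

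If no day in the interval between visits exceeds 4 loose stools, the visit answer is no throughout.

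**Which visits matter.** MMF ends 12 weeks after day 1. Visit 2 falls 4 weeks after visit 1, and visit 3 falls 11 weeks after day 1. The items at visits 2 and 3 therefore cover most of the MMF period, and visit 4 covers its tail. All three use the same wording.

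**Net effect on the count.** In one arm, let
- a = children meeting the 5.4.7 symptom definition,
- g = those among a who never exceed 4 loose stools on any day,
- s = children with at least one day of 5 or more loose stools who do not meet the 5.4.7 definition, for example because the episode was too short.

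Visit-item yes count = (a − g) + s. Its difference from a is s − g. The protocol gives none of a, g or s. The share of dose-rule children missed, g/a, could lie anywhere from 0 to 100%, and the sign of s − g is open.

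**The case against.** The strongest reply is that the event is not lost to the trial. Section 5.4.7 treats these episodes as adverse events, and Section 5.4.4 makes any new or worsened abnormality an adverse event, with no stool threshold. Section 7.2 collects adverse events from the first dose of study medication to visit 4, which spans the whole MMF period. Section 7.1.7 codes dose reduction and drug withdrawal, and Section 8.4 compares adverse event rates between the groups. This stands. What remains is a visit-based endpoint that can contradict the adverse event and dose records for the same child.

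A second reply is that the gap is narrow. One extra loose stool on one day between visits turns the answer to yes, and the form has no duration criterion, so it also picks up short episodes that 5.4.7 ignores. This stands too. A reader might infer that the diarrhea rate is biased in favour of MMF, or that a particular fraction of cases is missed. The protocol supports neither, because s − g has no determinable sign and there is no stool-frequency distribution from which to compute a fraction.

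A third reply is that an action threshold and a symptom query may serve different purposes. That would explain a form that is broader than the action rule. It does not explain one that requires more stools than the rule does.

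A reader might also extend the point to vomiting, where the dose rule says "vomiting (defined as a frequency of more than 2 times per day, lasting for ≥48 hours" and the form says "vomiting (defined as a frequency of more than 1 times per day". The numbers differ, but the form is positive from 2 a day and the dose rule needs 3 or more for 48 hours. Every case meeting the dose rule is already a yes, so no gap arises.

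**Conclusion.** The contradiction is real and nothing in the protocol resolves it. A child who never exceeds 4 stools a day can have MMF split, reduced or stopped for diarrhea and be recorded as free of diarrhea in the visit item behind the Section 2.2 endpoint. This rests on two readings: that the endpoint is taken from the side-effect item, and that watery stools count as loose.

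Its size is one stool-count value. The number of children and the net direction of any bias cannot be derived. It would also be too strong to read the mismatch as a threat to the trial's main conclusion. Section 2.2 says that toxicity is not tested confirmatorily, Section 8.4 treats secondary outcomes descriptively, and neither the primary endpoint nor the sample size uses this item. It should nevertheless be corrected, because the definition is fixed in the protocol and misclassified yes/no answers cannot be recovered.

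**What to change.** Reconcile Section 5.4.7 with the side-effect item in Section 6.1 so that any episode meeting the 5.4.7 symptom definition is a yes on the visit form. Say in Section 2.2 that this is the definition used for the endpoint. Which threshold applies is for the sponsor to settle.

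Use the same symptom-based definition in both arms. Do not make the answer depend on whether MMF was split, reduced or stopped: that trigger exists only in the MMF arm, and in an open trial it would make ascertainment differ between arms.

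The vomiting item needs no change on this ground. The cost is one eCRF definition, repeated across the visit descriptions, and one sentence in Section 2.2. No additional assessment is needed.

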1.3 Risk-benefit Assessment

MMF is effective in sustaining remission in patients with the frequently relapsing steroidsensitive nephrotic syndrome [13,14,19]. Therefore, after achieved remission the risk for immediate relapse is low, even during the initial manifestation of SSNS. If the number of patients with relapses after intervention is higher than expected (experimental intervention is inferior to control group), prednisone will be given anyway for induction of remission; the over-all

prognosis will therefore not be influenced. On the other hand, the patients in the experimental group have the potential to benefit significantly because of less glucocorticoid-associated toxicity.

The most frequently observed side effects of mycophenolate mofetil are gastrointestinal symptoms such as nausea, vomiting, stomach pain and diarrhea, hematological symptoms such as leukopenia, anemia and rarely thrombocytopenia and an enhanced susceptibility for infections. In general, these side effects occur more frequently and have a higher clinical significance, when MMF is administered in conjunction with other immunosuppressive medications such as cyclosporine or tacrolimus, as indicated after solid organ transplantation. When MMF is administered as monotherapy, for example in patients with frequently relapsing steroid-sensitive nephrotic syndrome, the frequency and severity of these side effects are markedly lower [13-18] and these side effects will be systematically evaluated during the study visits.

In order to acknowledge recent reported adverse events (hypogammaglobulinemia and bronchiectasia) in patients after solid organ transplantation and treated with MMF together with other immunosuppressive co-medication in the long-time run, these adverse events are monitored closely in the INTENT study (see 5.4.7.), despite these events are very unlikely to happen due to the short administration period.

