4.3 Exclusion Criteria

Subjects presenting with any of the following criteria will not be included in the study:

- Secondary nephrotic syndrome
- estimated glomerular filtration rate (eGFR) <90 ml/min x 1.73 m² BSA¹
- Ongoing treatment with systematically administered glucocorticoids or other immunosuppressive drugs at time of first episode of nephrotic syndrome.
- Hemoglobin concentration of ≤9 g/dL
- Leucocyte count of ≤2.500/µl
- Severe chronic gastrointestinal disease
- History of hypersensitivity to mycophenolate mofetil or to any drug with similar chemical structure or to any excipient present in the pharmaceutical form of suspension of mycophenolate mofetil (CellCept suspension®)
- Refusal of subject (please see also chapter 10.5)

Formula = (K * height [cm])/serum creatinine [mg/dl]

K = constant (determined by regression analysis) depends on the method of creatinine measurement:

- Jaffé method (photometric, kinetic measurement with picric acid) constant for age 1-13 years: K = 0.55 (Schwartz et al., 1976)
- Enzymatic measurement constant K = 0.413 (Schwartz et al., 2009)

¹ Estimated glomerular filtration rate

 Participation in other clinical studies or observation period of competing studies, respectively.

No subject will be allowed to enroll in this study more than once.

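### Section 5.4.7 misprints two MMF stopping rules: the haemoglobin level is given in g/L (equal to 0.8 g/dL), and the stop line for thrombocytes names leucocytes

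*Protocol*

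**What the plan says.** Protocol section 5.4.7 has three blood-count rules for MMF, built alike: a level at which the dose is halved and the value rechecked after 7-10 days, a level at which full dosing is tried again, and a level at which MMF is stopped.

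- **Haemoglobin.** The dose is halved at "hemoglobin concentration of ≤10 g/dL at visit 2 or visit 3". Full dosing returns on this condition: "Upon resolution (hemoglobin concentration ≥10g/dL), resumption of maintenance study drug dosing should be attempted". The stop line is "In case of hemoglobin concentration ≤8 g/L discontinuation of mycophenolate mofetil by investigator".
- **Leucocytes.** The dose is halved at ≤4.000/µL and resumed at ≥4.000/µL. The stop line begins "In case of leucocyte count ≤2.500" (per µL).
- **Thrombocytes.** The dose is halved at "thrombocyte count of ≤100.000" per µL and resumed at a thrombocyte count of ≥100.000/µL. The stop line begins "In case of leucocyte count ≤50.000" (per µL).

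Section 4.3 also states its haemoglobin limit in g/dL; children are excluded at "Hemoglobin concentration of ≤9 g/dL".

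**The concern.** Two of the three stop lines do not fit the rules they close. The haemoglobin stop changes unit from g/dL to g/L, which moves the printed level down by a factor of ten. The stop line in the thrombocyte rule refers to leucocytes, which already have their own stop level in the rule just above.

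These are safety thresholds for children aged 1 to 10 years, to be applied at about 45 sites. The two errors act in opposite directions:

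- **Haemoglobin.** The printed rule gives no usable stop level, so a child with severe anaemia would formally be due only a dose reduction and a recheck.
- **Thrombocytes.** The printed rule would stop MMF at once in almost every child who enters it, and the reduce-and-recheck step would be lost. Under section 4.4.1, a child taken off MMF should then receive the standard prednisone course.

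There is also an indirect link to the analysis. Section 8.3 counts a dose reduction of more than 50%, or an interruption of more than 3 days, as a major violation. Halving the dose stays within that limit; a stop usually does not.

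**Working it through.** **Inputs.** All levels come from Protocol section 5.4.7, except the exclusion level of 9 g/dL, which is from section 4.3.

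**Haemoglobin**

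1. Unit conversion, g/dL = (g/L) / 10: the printed stop is 8 / 10 = 0.8 g/dL.
2. Printed stop relative to the halving level: 0.8 / 10 = 0.08, or 8%.
3. Exclusion level relative to the printed stop: 9 / 0.8 = 11.25.
4. If g/dL was meant, the stop is 8 / 10 = 0.80, or 80% of the halving level, and lies 9 − 8 = 1 g/dL below the exclusion level.

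**Thrombocytes**

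1. Printed leucocyte level against the leucocyte stop: 50.000 / 2.500 = 20 times.
2. Printed leucocyte level against the leucocyte halving level: 50.000 / 4.000 = 12.5 times. A child whose leucocytes are high enough for full-dose MMF would still meet this stop, unless the count exceeded 50.000/µL.
3. If thrombocytes were meant: 50.000 / 100.000 = 0.50, or 50% of the halving level. The reduce-and-recheck band would be above 50.000 and up to 100.000/µL; the literal text removes this band.

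**The three rules side by side**

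| Rule | Halve at | Stop as printed | Stop / halve as printed | Stop / halve if corrected |
|---|---|---|---|---|
| Haemoglobin | 10 g/dL | 0.8 g/dL (8 g/L) | 8% | 80% (8 g/dL) |
| Leucocytes | 4.000/µL | 2.500/µL | 62.5% | no change needed |
| Thrombocytes | 100.000/µL | none (leucocytes 50.000/µL) | not defined | 50% (50.000/µL) |

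Once corrected, each rule has a stop at between 50% and 80% of its halving level.

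**Could this come from reading the PDF?** The word leucocyte in the thrombocyte rule cannot be a lost character. A dropped letter in the haemoglobin unit is conceivable, but g/dL is intact on the other lines of the same rule. A look at the source document would settle it.

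**When the rules apply.** The triggers are tied to visits 2 and 3. Visit 3 falls at week 11 (11 × 7 = 77 days after day 1, ± 7 days), and MMF ends at week 12 (12 × 7 = 84 days). A recheck 7-10 days after an on-time visit 3 falls on days 84 to 87, at or after the planned end of MMF. The reduce-and-recheck step therefore matters mainly after visit 2, and only in the MMF arm.

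**The case against.** The strongest reply is that neither line would be followed literally. A haemoglobin of 0.8 g/dL is an absurd threshold, and the neighbouring lines show the unit that was meant. In the thrombocyte rule the entry, recheck and resumption lines all name thrombocytes, so a site would hardly apply a leucocyte cut-off there. The investigator may also withdraw a child from treatment for adverse events (section 4.4.1). Section 5.4.7 itself leaves a temporary or permanent stop to the investigator for any MMF-related event, with support from clinical project management. The exposure window is short, and section 1.3 lists among the side effects of MMF "anemia and rarely thrombocytopenia". On this view the errors are editorial.

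Much of this stands. Literal application is unlikely, discretion is real, and any effect on membership of the per-protocol set is probably small. The intended values are inferred, and ratios ranging from 50% to 80% do not prove them.

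What does not follow is that the text can stay. Discretion supplies no level, and each site would have to infer a paediatric safety threshold for itself. Monitors who check adherence to the protocol have no usable standard in either line. Section 4.3 also admits children with haemoglobin just above 9 g/dL, who are already below the 10 g/dL halving level, so the haemoglobin rule covers values close to those at entry.

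**Conclusion.** Both lines are wrong as written and should be fixed. The printed haemoglobin stop is one tenth of the evident intention and, followed literally, would never take effect. The protocol contains no thrombocyte stop level at all. The haemoglobin error leans in the unsafe direction, the thrombocyte error towards stopping too often.

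This is a correction to safety wording. Sample size, significance level, power and the primary test do not depend on it, and no effect on the primary result is claimed. The number of children who might be affected cannot be derived from the protocol. The errors themselves rest on no assumption beyond the text being as printed; the intended levels of 8 g/dL and 50.000 thrombocytes per µL are inferences from the surrounding lines.

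**What to change.** Amend two lines in section 5.4.7: express the haemoglobin stop as ≤8 g/dL, and make the stop in the thrombocyte rule a thrombocyte count of ≤50.000/µL. The clinical leads should confirm both values against the source document first.

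Notify the sites. Check whether any eCRF check or site instruction carries the same errors; those documents were not available, so this is a precaution.

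The cost is a short amendment and a letter to the sites. Nothing changes in the sample size or the analysis.
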